7 STUDY PROCEDURES

Eligibility of each patient will be established prior to enrollment. Informed consent **MUST** be completed prior to receiving any study related procedures. Details regarding the schedule of procedures and observations are outlined below and in **Table 3**.

7.1 Vaccination Site Care

After the administration of the vaccine to the patient, the vaccination site will be covered loosely with a gauze bandage, using first aid adhesive tape to keep it in place.

The patient will be instructed as follows:

- Keep the vaccination site dry and cover the vaccination site with a waterproof bandage when bathing.
- Change bandage to the loose gauze bandage after bathing.
- **DO NOT** use a bandage that blocks all air from the vaccination site. This may cause the skin at the vaccination site to soften and wear away. Use loose gauze secured with medical tape to cover the site.
- **DO NOT** put salves or ointments on the vaccination site.

7.2 Unscheduled Visit

The Investigator may, at his/her discretion, arrange for a patient to have an unscheduled visit, especially in the case of AEs that require follow-up. If a patient is experiencing an AE considered by the Investigator to be possibly related to the study drug, an unscheduled visit should be performed; the unscheduled visit pages for the eCRF must be completed.

7.3 Schedule of Procedures and Observations

Clinical assessments will be performed every 4 weeks. Imaging with computed tomography (CT) or magnetic resonance imaging (MRI) will be performed according to standard of care. Performance status and AEs will be assessed at each clinical assessment until disease progression.

The schedule of procedures and observations for the INCB024360 cohorts in this study is summarized in **Table 3** below. Approximately ± 3 days are allowed for the schedule of procedures.

The schedule of procedures and observations for the exploratory cohort (with sirolimus) at Roswell Park site ONLY is summarized in Table 4.

Table 3. Schedule of Procedures and Observations (INCB024360 cohorts)

Study Event	Baseline ¹															3 Months, 6 Months, and 12 Months After Last Vaccine or dose of INCB
		Day 1	Cycle 1		Cycle 2		Cycle 3		Cycle 4		Cycle 5		Cycle 6		Cycle 7	
			Day 1	Day 2	Day 15	Day 1 ± 3 days	Day 2	Day 1 ± 3 days								
Informed Consent	X															
Medical History	X	X			X		X		X		X		X		X	
Physical Examination, vital signs and weight	X	X			X		X		X		X		X		X	
NY-ESO-1, TIL, PD-L1, and/or LAGE-1 Expression in Tumor Tissue ²	X															
HLA Typing (Historic HLA Typing is Permitted-low resolution) ³	X															
Disease Assessment ⁴	X								X							X
Hematology, PT/INR ⁶	X				X		X		X		X		X		X	
Chemistry ⁷	X				X		X		X		X		X		X	
Pharmacokinetic/Pharmacodynamic Sampling ⁸		X	X	X												
Performance Status (Appendix A)	X	X			X		X		X		X		X		X	
Tumor Markers ⁹	X	X			X		X		X		X		X		X	
Vaccination: DEC205mAb-NY-ESO-1 Fusion Protein (CDX-1401) given with Adjuvant Poly-ICLC		X			X		X		X		X					
																.1.1 Treatment discontinuation ¹³

Study Event	Baseline ¹	Cycle 1			Cycle 2			Cycle 3			Cycle 4			Cycle 5			Cycle 6			Cycle 7			.1.1 Treatment discontinuation ¹³	3 Months, 6 Months, and 12 Months After Last Vaccine or dose of INCB
		Day 1	Day 2	Day 15	Day 1 ± 3 days	Day 2	Day 1 ± 3 days	Day 2	Day 1 ± 3 days	Day 2	Day 1 ± 3 days	Day 2	Day 1 ± 3 days	Day 2	Day 1 ± 3 days	Day 2	Day 1 ± 3 days	Day 2	Day 1 ± 3 days	Day 2	Day 1 ± 3 days	Day 2		
Adjuvant Poly-ICLC (administered in clinic or at home by the patient)		X	X		X	X	X	X	X	X	X	X	X	X	X	X	X	X	X	X	X			
INC024360 ¹⁰		X	X	X	X	X	X	X	X	X	X	X	X	X	X	X	X	X	X	X				
Antibody Response: NY-ESO-1 ELISA and NY-ESO-1 Cellular Immune Response (T cell): ELISPOT and ICS ¹¹		X			X		X		X		X		X		X		X		X		X		X	
Urinary Pregnancy Test in Females of Childbearing Potential	X																							
Concomitant Medications	X ¹²	X			X		X		X		X		X		X		X		X		X			
Adverse Events	X	X			X		X		X		X		X		X		X		X		X			

Study Event	Baseline ¹	Cycle 1			Cycle 2		Cycle 3		Cycle 4		Cycle 5		Cycle 6		Cycle 7		.1.1 Treatment discontinuation ¹³	3 Months, 6 Months, and 12 Months After Last Vaccine or dose of INCB
		Day 1	Day 2	Day 15	Day 1 ± 3 days	Day 2												

- 1 To be performed within 28 days prior to the first vaccination.
- 2 Positive by either PCR or immunohistochemistry ((archived tissue (**Appendix F**) and/or frozen/fresh tumor tissue (**Appendix G**)). Documented historical NY ESO 1 positive results by IHC **or** PCR **or** serum antibody reactive with ESO are acceptable.
- 3 Refer to **Appendix H**
- 4 Including CT scan abdomen and pelvis, or PET/CT as described in **Section 8.5**; within 28 days prior to first vaccination. If patient early terms, CT will be performed at the PI's discretion.
- 5 Only 3 months and 6 month for those patients who have not experienced disease progression.
- 6 Hematology includes: CBC with auto differential, platelets. PT/INR for patients on anticoagulants.
- 7 Chemistry includes: glucose, urea nitrogen, creatinine, calcium, protein, albumin, bilirubin, AST, ALT, LDH, alkaline phosphatase.
- 8 Pharmacokinetic sampling is dependent upon cohort. Refer to **Section 7.7** for details.
- 9 Tumor markers to be obtained as per standard of care.
- 10 INCB024360 will be administered daily for 7 cycles.
- 11 Refer to **Section 7.5**.
- 12 Medications ongoing within 1 week prior to first dose of study drug.
- 13 Approximately 30 days after last study drug, con meds and AE's will be followed. Telephone contact is allowed.

Table 4 Schedule of Procedures/Observations (Exploratory cohort with Sirolimus-Roswell site ONLY)

Study Event	Baseline ¹	Cycle 1				Cycle 2				Cycle 3				Cycle 4				Cycle 5				^{1,2} Treatment discontinuation ¹²	3 Months, 6 Months, and 12 Months After Last Vaccine or dose of Sirolimus
		Day 1	Day 2	Day 15	Day 1 ± 3 days	Day 2	Day 1 ± 3 days	Day 2	Day 1 ± 3 days	Day 2	Day 1 ± 3 days	Day 2	Day 1 ± 3 days	Day 2	Day 1 ± 3 days	Day 2	Day 1 ± 3 days	Day 2	Day 1 ± 3 days	Day 2			
Informed Consent	X																						
Medical History	X	X		X	X		X		X		X		X		X		X		X		X		
Physical Examination, vital signs and weight	X	X		X	X		X		X		X		X		X		X		X		X		
NY-ESO-1, TIL, PD-L1, and/or LAGE-1 Expression in Tumor Tissue²	X																						
HLA Typing (Historic HLA Typing is Permitted-low resolution)³	X																						
Disease Assessment⁴	X																					X	X ⁵
Hematology, PT/INR⁶	X	X		X	X		X		X		X		X		X		X		X		X		
Chemistry⁷	X	X		X	X		X		X		X		X		X		X		X		X		
Performance Status (Appendix A)	X	X			X		X		X		X		X		X		X		X		X		
Tumor Markers⁸	X	X			X		X		X		X		X		X		X		X		X		

Study Event	Baseline ¹	Treatment Schedule										.12 Treatment discontinuation ¹²	3 Months, 6 Months, and 12 Months After Last Vaccine or dose of Sirolimus	
		Day 1		Cycle 1		Cycle 2		Cycle 3		Cycle 4		Cycle 5		
				Day 2	Day 15	Day 1 ± 3 days	Day 2	Day 1 ± 3 days	Day 2	Day 1 ± 3 days	Day 2	Day 1 ± 3 days	Day 2	
Vaccination: DEC205mAb-NY-ESO-1 Fusion Protein (CDX-1401) given with Adjuvant Poly-ICLC	X			X		X		X		X				
Adjuvant Poly-ICLC (administered in clinic or at home by the patient)	X	X		X	X	X	X	X	X	X	X			
Sirolimus⁹	X	X		X	X	X	X	X	X					
Antibody Response: NY-ESO-1 ELISA and NY-ESO-1 Cellular Immune Response (T cell): ELISPOT and ICS¹⁰	X			X		X		X		X		X		X
Urinary Pregnancy Test in Females of Childbearing Potential	X													
CMV PCR, Qualitative	X							X				X		
Lipid profile¹³	X		X	X				X						
Concomitant Medications	X ¹¹	X	X	X	X	X		X		X		X		
Adverse Events	X	X	X	X	X	X		X		X		X		

Study Event	Baseline ¹	Cycle 1			Cycle 2			Cycle 3			Cycle 4			Cycle 5			3 Months, 6 Months, and 12 Months After Last Vaccine or dose of Sirolimus
		Day 1	Day 2	Day 15	Day 1 ± 3 days	Day 2	Day 1 ± 3 days	Day 2	Day 1 ± 3 days	Day 2	Day 1 ± 3 days	Day 2	Day 1 ± 3 days	Day 2			

- 1 To be performed within 28 days prior to the first vaccination.
- 2 Positive by either PCR or immunohistochemistry ((archived tissue (**Appendix F**) and/or frozen/fresh tumor tissue (**Appendix G**)). Documented historical NY ESO 1 positive results by IHC **or** PCR **or** serum antibody reactive with ESO are acceptable.
- 3 Refer to **Appendix H**
- 4 Including CT scan abdomen and pelvis, or PET/CT as described in **Section 8.5**; within 28 days prior to first vaccination. If patient early terms, CT will be performed at the PI's discretion.
- 5 Only 3 months and 6 month for those patients who have not experienced disease progression.
- 6 Hematology includes: CBC with auto differential, platelets. PT/INR for patients on anticoagulants.
- 7 Chemistry includes: glucose, urea nitrogen, creatinine, calcium, protein, albumin, bilirubin, AST, ALT, LDH, alkaline phosphatase.
- 8 Tumor markers to be obtained as per standard of care.
- 9 4 cycles of Sirolimus 4mg/day will be given for 2 weeks, followed by 2 weeks off (each cycle = 28 days).
- 10 Refer to **Section 7.5**.
- 11 Medications ongoing within 1 week prior to first dose of study drug.
- 12 Approximately 30 days after last study drug, Con meds and AE's will be followed. Telephone contact is allowed.
- 13 Patients known from clinical history to have elevation of lipids and triglycerides will be followed per standard guidelines. Lipid profile will be obtained as lipid panel including: Cholesterol, triglycerides, LDL, HDL.

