Study Procedures and Observations	
Patients will have regularly scheduled study visits at the clinical site including physical exam, hematology, chemistry, and performance status-refer to Table 3 and Table 4 schedule of procedures and observations for specific time points..
 
Disease Assessment: Baseline, Cycle 4 Day 1, treatment discontinuation, and 3 and 6 months after last study drug dose.
 
Adverse Events: From first dose of study drug until 30 days (± 3 days) after the last dose of study drug.

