8 EFFICACY EVALUATIONS

8.1 Objective Tumor Response

All protocol-defined imaging studies must be performed at the investigative site or sponsor-approved facility using protocol-defined parameters. The same method of assessment and the same technique should be used to characterize each identified and reported lesion at baseline and during follow-up. RECIST 1.1 will be used to assess objective tumor response.

8.2 Target Lesions – PHASE 1

All measurable lesions up to a maximum of 2 lesions per organ and 5 lesions in total, representative of all involved organs, will be identified as target lesions and recorded and measured at baseline. Target lesions will be selected on the basis of their size. Lesions with the longest diameter (short axis for lymph nodes) and are ≥ 10 mm (CT and MRI), ≥ 15 mm lymph nodes, > 20 mm CXR and are for accurate repetitive measurements (either by imaging techniques or clinically) will be chosen. A sum of the longest diameter (short axis for lymph nodes) of all target lesions will be calculated and reported as the baseline sum diameters. This will be used as reference to further characterize the objective tumor response of the measurable dimension of the disease.

- **Complete Response (CR):** Disappearance of all target lesions. Any lymph nodes must have a reduction in short axis to < 10 mm. Changes in tumor measurements must be confirmed by repeat studies performed no less than 6 weeks after the criteria for response are first met.
- **Partial Response (PR):** At least a 30% decrease in the sum of diameters of target lesions, taking as reference the baseline sum diameters. Changes in tumor measurements must be confirmed by repeat studies performed no less than 6 weeks after the criteria for response are first met.
- **Progressive Disease (PD):** At least a 20% increase in the sum of diameters of target lesions, taking as references the smallest sum on study (this includes the baseline sum if that is the smallest on study). In addition to the relative increase of 20%, the sum must also demonstrate an absolute increase of at least 5 mm. The appearance of one or more new lesions is also considered progression.
- **Stable Disease (SD):** Neither sufficient shrinkage to qualify for PR nor sufficient increase to qualify for PD, taking as reference the smallest sum diameter while on study. Patients having a documented response with no confirmation of the response will be listed with stable disease.

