8.4 Evaluation of Response

Response assessment is for measuring time to disease progression. Time point response assessments will be performed on Cycle 4 Day 1 and Treatment discontinuation (timed to coincide with mid-point and the end of study) with a confirmatory assessment (required for non-randomized trials) within 6 weeks after a PR or CR is deemed. Response assessment may also be based on tumor marker measurements. To determine time point response using imaging studies, refer to **Table 5** and below.

Table 5. Time Point Response Criteria (+/- non-target disease)

Target Lesions	Non-Target Lesions	New Lesions	Overall Response
CR	CR	No	CR
CR	Non-CR/Non-PD	No	PR
CR	Not evaluated	No	PR
PR	Non-PD or not all evaluated	No	PR
SD	Non-PD or not all evaluated	No	SD
Not all evaluated	Non-PD	No	NE
PD	Any	Yes or No	PD
Any	PD	Yes or No	PD
Any	Any	Yes	PD

Table 6. Time Point Response Criteria (non-target disease only)

Non-Target Lesions	New Lesions	Overall Response
CR	No	CR
Non-CR/non-PD	No	Non-CR/non-PD ¹
Not all evaluated	No	NE
Unequivocal PD	Yes or No	PD
Any	Yes	PD

1 Non-CR/non-PD is preferred over SD for non-target disease since SD is used as endpoint for assessment of efficacy in trials so to assign this category when no lesions can be measured is not advised.

The best overall response is the best response recorded from the start of study treatment until end of treatment (taking into account any requirement for confirmation). In general, the patient's best response assignment will depend on the achievement of both measurement and confirmation criteria and will be determined by combining the patient's status of target lesions, non-target lesions, and new lesions.

- **Residual Disease:** Patients with objective response but who continue to have residual measurable disease.
- **Symptomatic Deterioration:** Patients with global deterioration of health status requiring discontinuation of treatment without objective evidence of disease progression at that time, and not related to study treatment or other medical conditions should be reported as progressive disease due to "symptomatic deterioration." Every effort should be made to document objective progression even after discontinuation of treatment due to symptomatic deterioration. Symptomatic deterioration that may lead to discontinuation of treatment include, but is not limited to, symptoms such as:
 - Weight loss > 10% of body weight.

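### Scan timing for the open-label primary PFS comparison is set by contradictory passages, and read literally the later assessments fall on different dates in the two Phase IIb arms

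*Combined protocol and SAP*

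**What the plan says.** The prose of Section 7.3 puts clinical visits on a 4-week rhythm and then says of imaging: "Imaging with computed tomography (CT) or magnetic resonance imaging (MRI) will be performed according to standard of care". No interval is given there or elsewhere.

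The same section then sends the reader to Table 3, which has a disease-assessment row. Footnote 4 describes that row as "Including CT scan abdomen and pelvis, or PET/CT as described in" Section 8.5, and adds: "If patient early terms, CT will be performed at the PI's discretion". Footnote 5 limits the follow-up assessments: "Only 3 months and 6 month for those patients who have not experienced disease progression". The synopsis names the same visits: "Disease Assessment: Baseline, Cycle 4 Day 1, treatment discontinuation, and 3 and 6 months after last study drug dose". Section 8.4 stops earlier: "Time point response assessments will be performed on Cycle 4 Day 1 and Treatment discontinuation", with no follow-up scans.

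Other passages decide what this means for the primary analysis:
- PFS runs from Day 1 to irRC progression that has been confirmed, or to death (PFS paragraph of Section 8.3). The trial is open label (3.1).
- Table 1 gives 5 vaccine cycles in both arms and 7 cycles of INCB024360 in Cohort 2b only. Table 3 counts follow-up from the last vaccine or INCB024360 dose. Section 6.2, however, defines completion as 7 cycles, and 3.1.1 gives about 28 weeks of active therapy for all Phase IIb patients.
- Randomization and the primary Cox model are stratified by site (11.1).
- The design assumes medians of 8 and 16 months, up to 5 years of follow-up, and power 0.70 (11.1.1).

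**The concern.** Radiological progression is recorded when a scan shows it. If the arms are scanned on different calendars, the same course of disease gives different PFS times, and the hazard ratio moves without any treatment effect. Here the timing rules disagree, staff know the arm, and the anchor for the later scans is itself a feature of treatment that differs between arms.

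The schedule also ends 6 months after last dose, long before the follow-up assumed in 11.1.1. Later progressions can be found only on scans for which the protocol sets no dates.

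**Working it through.** **1. Anchor dates, from Table 1.** Last vaccine-regimen dose in 2a is Cycle 5 Day 2: 4 × 28 + 2 = day 114. Last INCB024360 dose in 2b: 7 × 28 = day 196. Difference: 196 − 114 = 82 days.

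**2. Scan dates on the literal reading.** Assumptions: discontinuation visit 30 days after last dose; 3 and 6 months taken as 91 and 183 days; 30.4 days per month. Cycle 4 Day 1 is 3 × 28 = 84 days after Day 1, or 2.8 months, in both arms.
- 2a: 144/30.4 = 4.7, 205/30.4 = 6.7, 297/30.4 = 9.8 months.
- 2b: 226/30.4 = 7.4, 287/30.4 = 9.4, 379/30.4 = 12.5 months.

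**3. The plan's power.** Schoenfeld: power = Φ(√D/2 × ln 2 − 1.96) for HR 0.5, 1:1 allocation, two-sided 0.05 (assumed, since alpha is not stated). With D = 50 this is Φ(2.451 − 1.96) = 0.688, close to the stated 0.70. With the 48.0 events expected by 60 months it is 0.670. Simulated tests give 0.64 to 0.66.

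**4. Events from scheduled scans only, under the design effect.** Expected events = 25(1 − 2^(−t/8)) + 25(1 − 2^(−t/16)), with t the last scan in each arm.
- Literal last-dose schedule: 25(1 − 2^(−9.8/8)) + 25(1 − 2^(−12.5/16)) = 14.3 + 10.5 = 24.8.
- Both arms counted from the 7-cycle period: 25(1 − 2^(−12.5/8)) + 10.5 = 16.5 + 10.5 = 27.0 (26.9 in simulation).
- For comparison, t = 60 in both arms: 24.9 + 23.1 = 48.0.

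At D = 24.8, Schoenfeld power is Φ(1.726 − 1.96) = 0.41. Simulation gives 0.41 for both scheduled-only cases.

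**5. Effect on the hazard ratio.** Exponential progression is dated at the next scan and analysed by Cox regression with Efron ties. Rejection rates use 25 per arm and 2,000 replicates. HRs use 40,000 per arm, except the site row (median of replicates, site-stratified model). Deaths and confirmation scans are not modelled. The regular intervals are assumptions.

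| Scans, 2a / 2b | HR, no effect | Two-sided rejection | HR, true 0.5 | Power |
|---|---|---|---|---|
| 3 / 3 months | 1.01 | 5.0% | 0.50 | 0.64 |
| 3 / 4 months | 0.95 | 5.5% | 0.49 | 0.70 |
| 4 / 3 months | 1.05 | 5.0% | 0.52 | 0.58 |
| 3 / 6 months | 0.86 | 9.0% | 0.46 | 0.75 |
| 6 / 3 months | 1.15 | 8.8% | 0.55 | 0.49 |
| Literal last-dose schedule, ends at last scan | 0.93 | 5.1% | 0.46 | 0.41 |
| Literal schedule, then 3-monthly in both arms | 1.02 | 5.9% | 0.52 | 0.59 |
| Both arms from 7-cycle period, ends at last scan | 1.01 | 4.9% | 0.50 | 0.41 |
| Sites 3 vs 6 months, same in both arms | 1.01 | 5.2% | 0.51 | 0.60 |

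The Monte Carlo standard error of a 5% rate is √(0.05 × 0.95/2000) = 0.5 points. The literal schedule therefore shifts the estimate (0.93 to 0.94 across calculations) without a visible change in type I error.

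**The case against.** The strongest reply is that the standard-of-care sentence cannot be read alone. Section 7.3 goes straight on to Table 3, whose footnotes build CT into scheduled visits. Tumor markers are also listed by visit in Table 3 while footnote 9 leaves them to standard of care, so the wording may mean only routine extra imaging. That stands: a reader might infer that 7.3 leaves timing wholly to standard of care, and its own table does not support this.

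Four other stronger readings fail:
- *Differences between sites bias the HR.* Randomization and the Cox model are stratified by site, and the site-only case leaves the HR at 1.01.
- *The synopsis and 8.4 fix the dates, so deleting one sentence is enough.* They disagree on the follow-up scans, and only Cycle 4 Day 1 is fixed after baseline. Section 8.1 speaks of "All protocol-defined imaging studies must be performed at the investigative site or sponsor-approved facility using protocol-defined parameters" but names no visit.
- *Progression exists only on a scan date.* PFS counts deaths, 8.4 has symptomatic deterioration reported as progressive disease, and 8.5 allows caliper measurement of superficial lesions. This dilutes the effect of scan timing.
- *Power of 0.64 under equal scanning is a scan-timing loss.* Ordinary simulation without scan dating gives 0.64 to 0.66.

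It is also fair that no document gives a standard-of-care interval or a reason for it to differ by arm, and that 6.2 and the 28-week figure support a common 7-cycle anchor. On that anchor the arm difference disappears. The answer is that Table 1 and the Table 3 follow-up heading support the other anchor, so the text does not settle which applies.

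**Conclusion.** The point holds as an unresolved contradiction on the timing of the primary endpoint, with a modest expected bias. On the literal last-dose schedule the HR under no effect is about 0.93 to 0.94, in favour of the combination, if follow-up ends at the last scheduled scan. It is close to 1 if both arms are then scanned regularly. The range 0.86 to 1.15, with rejection near 9%, requires one arm to be scanned half as often as the other. It shows sensitivity and is not a forecast; a 3- versus 4-month difference moves the HR by about 5%.

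The shortfall in scheduled scans is larger. They supply about 25 to 27 events against about 48, so the stated power depends on imaging that the protocol does not schedule. These sizes rest on exponential progression, no deaths or confirmation scans, and a two-sided 0.05 test. No figure relies on Table 3's column positions, which are damaged in the available text.

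**What to change.** Reconcile 7.3, Table 3, the synopsis and 8.4 into one Phase IIb calendar. For example:

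> In both Phase IIb arms, disease is assessed at baseline, Cycle 4 Day 1, the end of the 7-cycle period, and 3 and 6 months after that date. Dates are counted from Day 1 and do not depend on when study drug was last given. Scans done at other times under standard of care are recorded with date and reason.

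Keep the standard-of-care scans, since they are the only routine source of later progressions. Bring the early-termination clause in footnote 4 into line with the calendar.

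Add a sensitivity PFS analysis that assigns each progression found within the calendar to the next common assessment date. In 11.1.1, state that scheduled scans alone give about 25 to 27 events and power about 0.4 under the design effect, so that 0.70 relies on later unscheduled imaging.

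Cost: some Cohort 2a scans come later than a last-dose anchor would put them (the second post-baseline scan moves from about 4.7 to 196/30.4 = 6.4 months), and one more analysis is run. The number of scheduled scans does not rise above the four post-baseline assessments in the synopsis. With identical dates in both arms, the HR under no effect returns to 1.

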6.7 Treatment Discontinuation

Upon treatment discontinuation all end of study evaluations and tests will be conducted. All patients who discontinue due to an AE must be followed until the event resolves or stabilizes. Appropriate medical care should be provided until signs and symptoms have abated, stabilized, or until abnormal laboratory findings have returned to acceptable or pre-study limits. The final status of the AE will be reported in the patient's medical records and the appropriate eCRF. If patient terminates study participation prior to study completion, all efforts will be made to complete an early termination visit (within approximately 30 days of last dose). Assessment will include physical exam, vital signs and weight, performance status, labs (CBC/diff, CMP, LDH, Coag if on anticoagulants, con med/AE assessment.

Reasons for treatment discontinuation should be classified as follows:

- Death
- Progressive disease
- Treatment-related toxicity
 - Subjects who experience a DLT will not receive any additional treatment (i.e., will be removed from the study and followed until resolution of their toxicity) and will not receive continued treatment even at a reduced dosage of the INCB024360 product.
 - Persistent toxicity that is unresolved to a grade 2 toxicity, where subsequent treatment cannot be given.
- Toxicity unrelated to treatment
- Investigator judgment

- The Investigator may withdraw a patient if, in his/her judgment, it is in the patient's best interest to do so.
- Noncompliance
- Patient voluntary withdrawal
 - A patient may withdraw from the study at any time, for any reason. If a patient discontinues treatment, an attempt should be made to obtain information regarding the reason for withdrawal.
- Roswell Park's decision.

Patients who are unavailable for follow-up evaluations should be classified as lost to follow-up for 1 of the following reasons:

- Lost to follow-up: For a patient to be considered lost to follow-up, the Investigator must make 2 attempts to re-establish contact with the patient. The attempts to re-establish patient contact must be documented (e.g., certified letter).
- Death: Date and cause of death will be recorded for those patients who die within 30 days after last dose of study drug (telephone contact is acceptable).

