8.3 Non-Target Lesions

All other small lesions (longest diameter < 10 mm or lymph nodes \geq 10 mm to < 15 mm short axis) and non-measurable lesions (i.e., leptomeningeal disease, ascites, pleural or pericardial effusion, inflammatory breast disease, lymphangitic involvement of skin or lung, blastic bone lesions, or abdominal masses / abdominal organomegaly identified by physical exam that is not measurable by imaging) should be identified as non-target lesions and indicated as present in the source documents at baseline. The general location will also be documented on the images drawing a regularly-shaped Region of Interest. Measurements of the non-target lesions will not be performed, but the presence or absence of each should be noted throughout follow-up and evaluation.

Those patients, who have no evidence of disease at the baseline, will be documented as no evidence of disease until progression of disease is documented per RECIST 1.1.

- **Complete Response:** Disappearance of all non-target lesions and normalization of tumor marker level, if applicable. All lymph nodes must be non-pathological in size (< 10 mm short axis).
- **Non-Complete Response/Non-Progressive Disease:** Persistence of 1 or more non-target lesion(s) and/or maintenance of tumor marker level above the upper limits of normal.
- **Progressive Disease:** Appearance of 1 or more new lesions or the unequivocal progression of existing non-target lesions. Although a clear progression of non-target lesions is exceptional, in such circumstances, the opinion of the treating physician should prevail and the progression status should be confirmed at a later time.
 - TUMOR RESPONSE ASSESSMENT BY IRRC – PHASE 2
- Tumor Response will be assessed by the Immune-related response criteria (irRC) as published by Wolchok et al. (68). Response is defined as irCR, irPR or irSD over a period of at least 4 weeks. Disease Control by irRC is defined as irSD or irPR or irCR.

PROGRESSION-FREE SURVIVAL (PFS)

Progression-free survival will be determined for each patient with time origin at the start of the treatment (day 1) until the first occurrence of confirmed progression by irRC or date of death if the patient dies from any causes before progression. Every effort will be made to follow patients for progression after they discontinue the study.

OVERALL SURVIVAL (OS)

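### CT at early termination is left to an unblinded investigator and contradicts the scheduled discontinuation assessment, so PFS can be selectively ascertained in patients who stop early

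*Combined protocol and SAP*

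**What the plan says.** **Text that makes the scan optional.** Table 3, footnote 4: "If patient early terms, CT will be performed at the PI's discretion". The same footnote appears under Table 4. For a patient who ends participation before study completion, Section 6.7 describes a visit within roughly 30 days of the last dose: "Assessment will include physical exam, vital signs and weight, performance status, labs (CBC/diff, CMP, LDH, Coag if on anticoagulants, con med/AE assessment". No imaging, disease assessment or tumor marker is listed.

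**Text that requires it.** Section 6.7 itself opens with "Upon treatment discontinuation all end of study evaluations and tests will be conducted". Section 8.4: "Time point response assessments will be performed on Cycle 4 Day 1 and Treatment discontinuation". The synopsis: "Disease Assessment: Baseline, Cycle 4 Day 1, treatment discontinuation, and 3 and 6 months after last study drug dose". None of these carries an exception.

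**Later assessment.** Footnote 5 limits post-treatment disease assessment: "Only 3 months and 6 month for those patients who have not experienced disease progression". The text of Section 7.3 adds "Imaging with computed tomography (CT) or magnetic resonance imaging (MRI) will be performed according to standard of care". Section 8.3 says "Every effort will be made to follow patients for progression after they discontinue the study", with no date, interval or modality.

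**Endpoint.** Section 3.1 describes the study as open-label. Under Section 8.3 a PFS event is confirmed irRC progression or death, and irPD needs two consecutive observations at least 4 weeks apart. The plan describes no PFS censoring rule and no blinded or independent review of progression.

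**The concern.** A site cannot follow all of these instructions. The footnote is the only one that deals specifically with imaging at early termination, so it is the one a site would probably apply. Whether an early terminator is scanned then depends on a physician who knows her arm. The only fixed on-treatment disease assessment after baseline is Cycle 4 Day 1, so a patient who stops before it may have no further protocol-mandated scan until 3 months after her last dose.

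If unscanned progressions differ between arms, the hazard ratio for the primary endpoint is biased. If they are equal, the trial mainly loses events, and its stated power is only 0.70.

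**Working it through.** **1. Dates.** With 28-day cycles, Cycle 4 Day 1 is 1 + 3×28 = Day 85. A patient stopping at Day 57 has not reached it. Her next scheduled assessment, if the discontinuation scan is skipped, is about Day 57 + 90 = Day 147.

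**2. The plan's own figure.** Inputs from Sections 11.1 and 11.1.1: 25 per arm, medians of 8 and 16 months (HR 0.5), constant hazard, 9-month accrual, up to 5 years of follow-up, simulated power 0.70. Alpha is not stated; I assume two-sided 0.05. I take the 8-month arm to be vaccine alone (2a), since that is the comparator in the randomized design. With 60 months in total, expected events are 47.5. Schoenfeld: power = Φ(√(d/4)·|ln HR| − 1.96) = Φ(√(47.5/4)×0.693 − 1.96) = Φ(0.43) = 0.67. A simulated log-rank test gives 0.65. All 50 events would give 0.69. The stated 0.70 is therefore roughly what full ascertainment yields and leaves no margin for lost events.

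**3. Progressions exposed to the gap.** P(progressed by t) = 1 − 2^(−t/median), with 30.44 days per month.

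| Time | 8-month arm | 16-month arm |
|---|---|---|
| Day 57 | 15.0% | 7.8% |
| Day 113 | 27.5% | 14.9% |
| 7 cycles (196 days, 6.44 months) | 42.8% (10.7 of 25) | 24.3% (6.1 of 25) |

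**4. Illustration with early stopping.** Assumptions, none of them from the documents: 5% of 2a and 20% of 2b stop early, uniformly over Days 29–113; stoppers have twice the hazard; half of the progressions present at stopping are missed. Large-sample Cox model, 60 months:

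| What follows after stopping | HR | Events of 50 |
|---|---|---|
| Full follow-up | 0.55–0.56 | 48.4 |
| Scan at +3 months, then followed | 0.55 | 48.4 |
| Scans at +3 and +6 months, then censored | 0.53 | 45.6 |
| No later assessment | 0.50 | 42.8 |

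With 10%/30% stopping and three times the hazard, the same four rows give 0.62, 0.61, 0.57 and 0.51. If stopping is unrelated to prognosis, the HR stays at 0.49–0.50 even with no later assessment, and the loss is in events (about 48 down to 42–43).

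For scale, SE(ln HR) ≈ 2/√48.4 = 0.29. The move from 0.554 to 0.530 is ln(0.554/0.530) = 0.044, about 0.15 SE. The move to 0.502 is 0.099, about 0.34 SE.

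**5. Direction.** A second model never images a share of the progressions in the 6.44-month window and censors them. Assumed share: up to 30%.

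| Share missed | True HR 1: median HR (false positives favoring the combination) | True HR 0.5: median HR (power) |
|---|---|---|
| None | 1.00 (2.8%) | 0.495 (0.65) |
| 20% or 30%, combination only | 0.91 or 0.87 (5.6% or 7.7%) | 0.46 or 0.44 (0.73 or 0.76) |
| 20% or 30%, vaccine alone only | 1.10 or 1.16 (1.4% or 0.8%) | 0.53 or 0.56 (0.53 or 0.47) |
| 10% to 30%, both arms | 1.00 (2.8–2.9%) | 0.49–0.50 (0.63–0.60) |

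Unequal loss moves the HR either way; equal loss leaves it in place and costs power.

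**The case against.** Section 6.7 can be read as separating two groups. Everyone who discontinues treatment gets the full set of evaluations; the short list applies only to those who end participation. If the footnote means the second group, a patient who stops drug for toxicity and remains in follow-up keeps her discontinuation scan, and a patient who truly leaves cannot be compelled to have one. This is a fair reading, but the text does not settle it. The documents also blur the distinction: Section 6.3 has patients with unresolved toxicity withdrawn from the study, and Sections 6.3.1 and 6.7 have patients with a DLT removed from it.

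A second objection is that the 3- and 6-month assessments, 4-weekly clinical assessments and standard-of-care imaging remain. This stands for patients still followed, and it is why the illustration shrinks to 0.53, or to almost no shift if follow-up continues. Standard-of-care imaging, however, sets no fixed schedule.

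A reader might infer that the gap systematically favors the combination, because 2b adds a drug, runs 7 cycles rather than 5 and is subject to the DLT removal rule. The documents do not support that. They give no stopping rate and no censoring rule. The DLT period is 28 days, and Phase IIb allows interruption and dose reduction. Both arms are still in the vaccination cycles over Days 29–113, so the difference in length hardly acts there. A reader might also take 0.50 as the expected distortion; that figure requires that nobody who stops is ever assessed again, contrary to the synopsis and footnote 5.

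**Conclusion.** The contradiction is in the text and concerns ascertainment of the primary endpoint. Progression can be selectively ascertained in early terminators; the documents do not show that it will be. For patients who stop drug but stay in follow-up the cost is mainly late detection; for those who leave, the progression may never be recorded. Size and direction are unknown. Under the assumed 5%/20% stopping with doubled hazard, the HR moves from 0.55–0.56 to about 0.53 when only the scheduled 3- and 6-month scans follow, a small shift against the trial's own imprecision. With prognosis-neutral stopping it hardly moves. This should be fixed because the correction is cheap and the scan is already called for elsewhere, not because a large bias has been demonstrated.

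**What to change.** For Phase IIb:

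- Delete the discretion sentence in Table 3 footnote 4.
- Add the already scheduled disease assessment to the early-termination list in Section 6.7, waived if a scan was done within about 4 weeks.
- State that patients who stop treatment without progression keep the scheduled 3- and 6-month assessments.

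With these changes, the ambiguity between stopping drug and leaving the study no longer affects whether a scan is due.

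Cost: an amendment to one footnote and one list, plus one clarifying sentence. No new time point is created, because the synopsis and Section 8.4 already schedule these assessments. A few more CTs will actually be performed, and some patients who leave the study will decline, so the gap narrows rather than closes. A single discontinuation CT also does not by itself meet the two-observation requirement for confirmed irPD.
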